2.2.6 FULFILLING AN UNMET NEED

[figure not shown]
The results from the above studies demonstrate the need for new innovative, non- or minimally-invasive tests to replace the invasive tests and to improve the accuracy of current non- or minimally-invasive tests. The data suggest that the HepQuant SHUNT Test can potentially fulfill this unmet need. Our proposed validation study is a prospective multi-center study of sufficient power to define the cutoff for DSI for both ruling in and ruling out large esophageal varices.

2.2.7 INTEGRATING THE HEPQUANT SHUNT TEST INTO CLINICAL PRACTICE

The current and proposed paradigms for assessing a person with CLD for varices are shown in Figure 2.

Current Practice. A physician or care provider initiates a workup to include a medical history, physical examination, and standard laboratory tests (CBC, AST, ALT, Alkaline phosphatase, bilirubin, albumin). The results of this initial assessment may raise suspicion that a patient has chronic liver disease, including cirrhosis. Typically, the care provider would test for etiology of liver disease, such as viral hepatitis (HCV-Ab, HBsAg, HBcAb, others), iron overload (iron, TIBC, ferritin), autoimmune disease (ANA, others), and assess the liver by imaging with a standard ultrasonographic exam (echogenicity as surrogate for fatty liver or fibrosis). Additional tests to stage disease severity and need for EGD screening for varices could include elastography, liver biopsy, radiologic imaging, measuring HVPG, or combinations of these tests. The most commonly accepted noninvasive approach is the combination of LSM plus platelet count. **Figure 2** compares the results with no additional risk assessment, risk assessment by LSM plus platelets from published literature, to risk assessment using DSI based on results from the HALT-C Training dataset. The goal is to better inform the decision to avoid or perform EGD screening for varices.

Figure 2: DSI as an Aid in the Decision to Avoid or Perform EGD for Screening for Varices

HepQuant Paradigm. In the HepQuant paradigm, a patient with CLD meets criteria for selection for EGD and the HepQuant SHUNT test is performed. DSI \leq 18.3, implying low likelihood of large esophageal varices, might aid in the clinician's decision to avoid or proceed with EGD. For DSI >18.3, the higher the DSI the higher the risk for large esophageal varices and the greater the urgency to perform EGD.

If the HepQuant SHUNT Test indicates low risk, e.g, DSI \leq 18.3, endoscopy may be avoided, and standard clinical follow-up may be all that is warranted. The results for DSI \leq 18.3 from HALT-C (Sensitivity 95%, Specificity 54%, NPV > 99%, NLR 0.09, and FNR < 1.0%) suggest that application of DSI could lower the number of unnecessary EGDs by 50% and reduce the false negative rate by greater than two thirds (**Figure 2**).

With increasing DSI beyond 18.3, the likelihood of large esophageal varices increases – the clinician could incorporate DSI into his decision regarding urgency for endoscopic screening. Endoscopic screening for varices is increasingly warranted as DSI increases.

In other studies of DSI, DSI increases in parallel with the increase in fibrosis and progression to cirrhosis and predicts risk for clinical outcome (ascites, spontaneous bacterial peritonitis, encephalopathy, variceal hemorrhage, and liver-related death) (40-50). In the HALT-C Trial, the prototype for the HepQuant SHUNT test outperformed liver biopsy and standard laboratory tests in likelihood of cirrhosis and varices and in identifying the patients at high risk for clinical outcomes (83-86). With one parameter from the HepQuant SHUNT Test, DSI, a clinic provider could counsel a patient on risk for large esophageal varices to aid in the decision to perform EGD.

2.3 Risk/Benefit Assessment

2.3.1 KNOWN POTENTIAL RISKS

- 1. Risks from the Test Compounds
 - a. Allergic reaction to cholate compounds (theoretical none yet reported)
 - b. Allergic reaction to human serum albumin (HSA)
 - Reactions could include:
 - i. rash
 - ii. having a hard time breathing
 - iii. wheezing when you breathe
 - iv. sudden drop in blood pressure
 - v. swelling around the mouth, throat, or eyes
 - vi. fast pulse
 - vii. sweating
 - viii. severe reactions are very rare but a severe reaction (called anaphylaxis) can lead to profoundly low blood pressure and even death
- 2. Risks from the Indwelling catheter
 - a. Pain with placement of catheter
 - b. Thrombosed vein
 - c. Hematoma
- 3. Risk of Phlebotomy
 - a. Localized pain
 - b. Bruising
 - c. Occasional lightheadedness,
 - d. Fainting
 - e. Infection at the site (rare)
- 4. Risk of Fasting
 - a. Dizziness
 - b. Headache
 - c. Stomach Discomfort
 - d. Fainting

Risk of Test Administration

As stated above, over 1600 HepQuant SHUNT tests have been performed in over 700 subjects without any reports of adverse events, serious adverse events, or serious unexpected serious adverse events.

Cholates, labeled with stable (nonradioactive) isotopes, occur naturally and are not known to have any deleterious or adverse effects when given intravenously or orally in the doses used in HQ tests. The serum cholate concentrations that are achieved by either the intravenous or oral doses are similar to the serum concentrations of bile acids that occur after the ingestion of a fatty meal. Because cholates are naturally occurring with a pool size in humans of 1 to 5 g, the 20 and 40 mg doses of labeled cholates used in the HQ tests are unlikely to be harmful to a fetus. However, the effects of these compounds on the fetus are not definitively known. Possible adverse event associated with the cholate test compounds may include: allergic reaction.

The two cholates used in the HepQuant SHUNT test for this study are labeled with stable (non-radioactive) forms of carbon and hydrogen that are found in nature and can be measured in blood. These forms of cholate have been used with FDA INDs (65121 and 65123) since 2002, and their use in humans has been monitored since that time.

To date, the cholates used in this study have not been associated with any allergic reactions or side effects. However, they are still considered experimental and there may be unknown risks.

Cholate, in a dose of 15 mg kg⁻¹ d⁻¹, is FDA-approved for the treatment of pediatric liver diseases, even in neonates as young as 3 weeks. It is safe in these high doses even after several years of administration (87,88).

There are no known immediate or long-term physical, psychological, social, legal, economic, or other risks to participants related to the labeled cholates.

Human serum albumin is mixed with the 13C-cholate for intravenous injection. Some individuals may have a known reaction to serum albumin and will be excluded from this study. Possible adverse event from the HSA may include: allergic reaction (89-93).

Rare Hypersensitivity Reactions have been reported to human serum albumin preparations and include anaphylaxis, severe anaphylaxis or anaphylactoid reactions, fever, chills, rash, urticaria, pruritus, angioneurotic edema, and erythema or flushing. Individuals who are hypersensitive to albumin preparations, any ingredient in the formulation, or components of the containers should be excluded from this study.

Risk of Transmissible Diseases in Plasma-derived Preparations. Because human albumin is prepared from pooled human plasma, there is a potential to pass human viruses (e.g., hepatitis viruses, HIV) to the recipient and may carry a risk of transmitting Creutzfeldt-Jakob disease (CJD) or its variant CJD (vCJD). Through donor plasma screening and specific procedures like pasteurization to eliminate or inactivate any possible causes have reduced, but not entirely eliminated, the risk of transmission of disease causing agents. Risk of transmission of viral disease with plasma-derived human albumin is considered extremely remote. No causes of transmission of HBV, HCV, or HIV have been documented following use of commercially available human albumin. There are no documented cases of CJD or vCJD transmitted through plasma-derived preparations (including plasma-derived human albumin); theoretical risk for transmission of CJD with commercially available human albumin is considered extremely remote.

However, no purification method has been shown to be totally effective in removing the risk of viral infectivity from plasma-derived preparations and because new blood-borne viruses or other disease agents may emerge which may not be removed or inactivated by current manufacturing processes, the risks of human albumin are not entirely known.

Risk of Indwelling Intravenous Catheter. Placing the indwelling intravenous catheter will cause minor pain and discomfort. With any blood draw, there is a small risk of hematoma and a very small risk of a blood clot (1 in 100) or infection (1 in 1000). HepQuant has performed the HepQuant SHUNT test or the prototypical dual cholate research test on over 700 individuals and most had the test multiple times. There has never been a test-related serious adverse event - the risk from the test is very small. Possible adverse event from the placement of an indwelling catheter may include: hematoma at injection site.

Risk of Phlebotomy. Drawing blood from a vein may cause local pain, bruising, occasional lightheadedness, fainting, and very rarely, infection at the site of the blood draw.

Risk of Fasting. Fasting could cause dizziness, headache, stomach discomfort, or fainting.

Pregnancy. Because cholates are naturally occurring with a pool size in humans of 1 to 5 g, the 20 and 40 mg doses of labeled cholates used in the HQ tests are unlikely to be harmful to a fetus. However, the effects of these compounds on the fetus are not definitively known (see Section 8.4.10).

Unknown or Unexpected Risks. The two cholates used in the HepQuant SHUNT test have been registered with the FDA since 2002, and their use in humans has been monitored since that time and IND annual reports filed with FDA. Given the endogenous and ubiquitous nature of the cholates, we do not anticipate any unexpected risks. However, the compounds are still considered experimental and there may be unknown risks.

Risk of False Positive Test. The intended population, CLD patients scheduled for EGD for screening for varices, would undergo the EGD independent of a positive DSI test. There is no clinical consequence of a false positive DSI.

Risk of False Negative Test. The study design encompasses a broad spectrum of CLD etiologies and severity of disease. The targets for sensitivity and specificity as defined in Section 9.0 below, for the expected prevalence of large varices of approximately 20%, will ensure an acceptably low FNR when compared to current SOC. Subjects in the clinical trial will not be exposed to this risk, as the physician performing the EGD will be blinded to the results of the HepQuant test, and the EGD will performed regardless of the test outcome.

2.3.2 POTENTIAL COMPLICATING MEDICAL ISSUES

Use of Concomitant Medications. Non-selective beta blockers, ARB and/or ACE inhibitors could affect the blood flow to the liver, and therefore could affect the flow of the HepQuant SHUNT cholate test compounds into the liver as well. If the flow of blood to the liver was altered by these drugs, it could impact the SHUNT test results. Additionally, because individual patients may take different amounts of these drugs, we are unable to correct for the different concentrations and their impact on blood flow to the liver. As such, subjects who are currently taking either a non-selective beta blocker, ARB and/or an ACE inhibitor will be asked to delay taking their normal morning dose the day of their testing and until the 90-minute test is completed. Delaying these medications could cause a temporary elevation in blood pressure but the risk would be minimal, like that of subjects that delay doses of medications in everyday life. Patients will therefore be instructed to immediately take their morning dose after the final 90-minute blood draw has been completed. Possible adverse event from delaying taking ACE or ARB inhibitor and/or Non-Selective Beta Blockers may include: minimal change in blood pressure.

Medical or Surgical Conditions and might interfere with interpretation of test results. Subjects with serious intercurrent medical or surgical illness, such as acute myocardial infarction, acute cerebral hemorrhage, sepsis, or other immediate life-threatening illness are excluded. Subjects with extensive resection of large segments of small intestine (short gut) or severe gastroparesis might not be able to absorb the oral dose of d4-cholate and are excluded.

2.3.3 THE MANNER IN WHICH RISKS WILL BE MINIMIZED

Any subject that does not meet all of the inclusion criteria, and none of the exclusion criteria, will not be enrolled in this study.

All sites coordinators and other staff are trained by HepQuant personnel on the use of the HepQuant SHUNT Kit. Training includes the review of all warnings and precautions. Site personnel record any medications the subject is taking and whether or not specific medications have been withheld per the IFU.

The site personnel administering the HepQuant SHUNT test are trained healthcare professionals with substantial experience with phlebotomy, use of indwelling catheters, and mixing drug substances for patient administration. All sites must undergo training prior to use of the HepQuant SHUNT kit. Training is recorded.

2.3.4 ASSESSMENT OF POTENTIAL RISKS AND BENEFITS

Assessment of known potential risks. The potential risks of the administration of the HepQuant SHUNT Test are:

• IV catheter and blood sampling: Standard risk of local pain, hematoma. Rare risk for infection or thrombosis – although none reported to date.

• Albumin: Very rare hypersensitivity reactions reported with risk <1:10,000. No hypersensitivity reactions reported to date with the injectable mixture of albumin:13C-cholate.

There are no known risks associated with cholate, and no known AEs or SAEs associated with the stable isotopes or formulations of cholate employed in the combination product.

The above safety profile supports the conclusion that administration of the HepQuant SHUNT Test exposes subjects to minimal risk. To further minimize risk, the test will be administered in research or infusion centers with appropriate supervision, nursing support and expertise, and availability of emergency care and procedures.

Another potential risk is the risk of inappropriate clinical decisions based upon the results of the HepQuant SHUNT Test. In this study, the decision to perform EGD is made prior to enrollment of the patient by clinicians using standard criteria. The results of the HepQuant SHUNT test are not being used for any clinical decisions in the SHUNT-V study.

As stated above, the criteria for validation of DSI 18.3 for "Rule Out" of large esophageal varices will ensure an acceptably low FNR.

Recording and Reporting of AEs, SAEs, SUSARs. All AEs, SAEs, and SUSARs will be recorded and evaluated for association with the HepQuant SHUNT test. Safety data and any associated regulatory reporting obligations for individual or periodic safety reports will be reported to the appropriate authorities and clinical investigators and applicable IRB/EC, in compliance with all applicable laws and the requirements of the IRB/EC.

In the HALT-C Trial, reporting of AEs, SAEs, and SUSARs was performed by New England Research Institute (NERI) and the DSMB for the Trial. No AEs, SAEs, or SUSARs related to the HepQuant SHUNT research prototype (dual cholate test) were reported.

Justification for conduct of this study. The risks to the individual participant are minimal. However, the information gained from the DSI cutoff has implications for potentially improving the care and management of CLD patients. The main benefit is more accurate assessment of the likelihood for large esophageal varices.

The information regarding the DSI cutoff and negative likelihood of large esophageal varices could assist the trained clinician by providing additional data that could help in the decision to avoid or defer EGD. Of course, the clinician will consider the algorithm associating DSI with varices, incorporate other factors, and use his own judgment, about the decision to avoid or defer EGD.

3 OBJECTIVES AND ENDPOINTS

OBJECTIVES	ENDPOINTS	JUSTIFICATION FOR ENDPOINTS
Primary		
The primary objective of this study is to validate DSI ≤18.3 for identifying subjects with CLD selected for future EGD for variceal screening or surveillance who are not likely to have large esophageal varices ("Rule Out").	The endpoint for the primary objective is the negative likelihood ratio (NLR) for large esophageal varices. The performance goal for validation of DSI ≤18.3 is the upper limit of the confidence interval (CI) for NLR to rule out NLR > 0.52, in addition the observed sensitivity must be > 0.85. The confidence level for the confidence interval will be adjusted in order to maintain a one-sided type I error rate of 0.025 as described in section 9.5.1.	Primary: The current minimally- invasive practice using liver stiffness measurement (LSM) by transient elastography (TE) plus platelet count, yields NLRs from 0 to 1.1. A critical value (cv) of 0.27 for NLR represents the average of results for these studies in ruling out large esophageal varices. The study is designed for superiority over current practice.
Secondary		
The secondary objective is to perform logistic regression analysis of the probability of large esophageal varices for DSI > 18.3. In the HALT-C Training Dataset the probability of large varices increased in proportion to increasing DSI in subjects with DSI above 18.3.	The secondary endpoint is the significance of the logistic regression equation for the relationship of DSI >18.3 to probability of large esophageal varices.	Secondary : Predicted probability of large varices versus DSI will be analyzed by logistic regression analysis and affiliated statistical tests of the significance of the association between the continuous DSI score and risk of large varices. These analytical results will be evaluated using a calibration table in which the prevalence of large varices is tabulated by DSI quartile. A clinician knowing that a high DSI has a high probability of large varices could enhance his sense of urgency to perform EGD.
Tertiary/Exploratory		
Exploratory objective 1 is to generate and evaluate the AUROC (by c-statistic) for DSI in likelihood of large esophageal varices over the full range of DSI. One goal of this analysis is to define the diagnostic performance (sensitivity, specificity, PPV, NPV, NLR, FNR, miss rate ³) for DSIs below and above the validated DSI of 18.3. This	The endpoint for exploratory objective 1 is the AUROC (c-statistic) for DSI in the likelihood of large esophageal varices over the full range of DSI.	Exploratory 1: The purpose of this analysis is to provide upside and downside performance of DSI around the validated cutoff of DSI 18.3. This analysis will yield a table of sensitivities, specificities, NPVs, PPVs, NLRs, FNRs, and miss rates over the given range of DSI that

³ In this protocol, FNR is defined as 1-NPV and miss rate is defined as 1-Sensitivity. See the footnote in Section 1.1 for a discussion of these two measures.

ENDPOINTS	JUSTIFICATION FOR ENDPOINTS
	could be included in a package
	insert to help the clinician interpret
	a given DSI result.
The endpoints for exploratory	Exploratory 2: Linking DSI to small
objective 2 are the c-statistics for the	or any size of esophageal varices
AUROCs for DSI in the likelihood of	may aid the decision regarding
small or any size of esophageal	closer clinical followup.
varices.	
The endpoints for exploratory	Exploratory 3: Linking STAT, which
objective 3 are the c-statistics for the	is derived from the 60-minute time
AUROCs for STAT in the likelihood of	point of the orally administered d4-
large, small, or any size of esophageal	cholate, to large esophageal varices,
varices. The c-statistics for STAT will	small varices, or varices of any size
be compared to the c-statistics for DSI.	could provide a simple, oral only,
	"drink and draw" test at the point-
	of-care in the clinic.
	The endpoints for exploratory objective 2 are the c-statistics for the AUROCs for DSI in the likelihood of small or any size of esophageal varices. The endpoints for exploratory objective 3 are the c-statistics for the AUROCs for STAT in the likelihood of large, small, or any size of esophageal varices. The c-statistics for STAT will

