Avoiding unnecessary EGD is a goal of screening. The percentage of unnecessary EGDs is defined by the number of cases with no or small varices that underwent EGD that would have avoided EGD by application of selection criteria. A meta-analysis of the 10 published studies suggested that application of BAVENO VI criteria might reduce screening or surveillance EGDs by 7% to 30% (6). Each of the 10 studies applied different combinations of cutoffs for platelet count (>100,000 μ L-1, >120,000 μ L⁻¹ or >150,000 μ L⁻¹) and LSM (<20 or <25 kPa). The individual study results were pooled, and the pooled estimates were sensitivity 93%, specificity 30%, negative predictive value (NPV) 97%, positive predictive value (PPV) 14%, negative likelihood ratio (NLR) 0.22, positive likelihood ratio (PLR) 1.33 (Table 2), and false negative rate (FNR) 3%. The analysis also revealed that 21 of 319 (6.5%) large varices needing treatment were missed (6). Another review further highlighted the relatively low rate of reduction in EGDs (20% overall) and unacceptably high FNR and rate of missed large varices or varices needing treatment (4).

Study	Prevalence	ТР	FN	FP	TN	Sens	Spec	PPV	NPV	FNR	PLR	NLR
Abraldes	0.15	54	3	238	84	0.95	0.26	0.18	0.97	0.03	1.28	0.20
Ahmed	0.11	49	3	318	108	0.94	0.25	0.13	0.97	0.03	1.26	0.23
Chang	0.08	11	3	128	31	0.79	0.19	0.08	0.91	0.09	0.98	1.10
Ding	0.10	26	0	138	107	1.00	0.44	0.16	1.00	0.00	1.78	0.00
Maurice	0.05	13	2	195	100	0.87	0.34	0.06	0.98	0.02	1.31	0.39
Paternostro	0.21	19	0	61	10	1.00	0.14	0.24	1.00	0.00	1.16	0.00
Puigvehi	0.15	45	10	174	139	0.82	0.44	0.21	0.93	0.07	1.47	0.41
Silva	0.18	20	0	80	12	1.00	0.13	0.20	1.00	0.00	1.15	0.00
Thabut	0.08	49	0	445	156	1.00	0.26	0.10	1.00	0.00	1.35	0.00
Tosetti	0.08	12	0	95	39	1.00	0.29	0.11	1.00	0.00	1.41	0.00
Pooled Totals	0.11	298	21	1872	786	0.93	0.30	0.14	0.97	0.03	1.33	0.22
Means of Studies	0.12	30	2	187	79	0.94	0.28	0.15	0.98	0.02	1.32	0.23
SD of Studies	0.05	17	3	119	52	0.08	0.11	0.06	0.03	0.03	0.21	0.35
HALT-C	0.10	21	1	89	106	0.95	0.54	0.19	0.99	0.01	2.09	0.08

Table 2: Diagnostic Performance of LSM + Platelet Count versus DSI for Likelihood of Large Esophageal Varices

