9.1 Statistical Hypotheses

9.1.1 PRIMARY EFFICACY ENDPOINT (DSI ≤18.3 "RULES OUT" LARGE ESOPHAGEAL VARICES).

For each subject, the primary endpoint is the presence of large varices based on EGD examination. The primary estimands are NLR and sensitivity which then define the standard for diagnostic accuracy of DSi as a rule-out test for large varices. A primary objective is to determine whether the NLR for DSI \leq 18.3 is an improvement over the average value for NLR from 10 published studies of 2977 cases of the use of LSM plus platelet count in likelihood of large esophageal varices. Improvement will be decided if the confidence interval for the observed NLR rules out NLR > 0.52, which corresponds to the observed NLR being smaller than the approximate critical value of cv= 0.27. With this partition of the ROC outcome space, the study will conclude that the diagnostic accuracy of DSI < 18.3 is acceptable if the observed NLR is smaller than that observed in most previously published studies (**Figure 10**). The null hypothesis of NLR = 0.52 is chosen to demonstrate improvement over the diagnostic accuracy of tests evaluated in the 10 published studies of 2977 cases.

⁶ A single interim analysis is planned after the trial data set has compete DSI and EGD measurements on a minimum of 250 participants as described in Section 9.5.1.

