9.2 Sample Size Determination

9.2.1 PRIMARY EFFICACY ENDPOINT: SAMPLE SIZE AND POWER

Based on NLR

The trial sample size was evaluated and selected to assure adequate statistical power that the upper limit of the 95% CI for NLR will be smaller than 0.52. For design purposes we evaluate power and sample size using the variance from Table 9 equation E under the hypothesis that NLR = 0.20 with sensitivity = 0.90, specificity = 0.50, and 20% prevalence of large varices (i.e., 80 subjects with large varices = 0.2x400). A sample size of 400 participants (80 with large varices, 320 without) was selected to provide adequate power based on the following power characteristics:

		Power	for variou	ıs sample	sizes
NLR	FNR	380	400	420	440
0.20	0.048	0.78	0.80	0.82	0.84
0.19	0.045	0.82	0.84	0.86	0.87
0.18	0.043	0.86	0.88	0.89	0.91
0.17	0.041	0.89	0.91	0.92	0.93
0.16	0.038	0.92	0.93	0.94	0.95
0.15	0.036	0.95	0.96	0.96	0.97

Table 10: Initial Power Analysis for Selection of N-400

In this analysis 400 subjects provide over 80% probability/power of rejecting the rule-out hypothesis of NLR > 0.52 when the true NLR is smaller than 0.20. From Table 9 equation D, NLR = 0.2 corresponds to FNR = 0.048; thus, the trial has more than 80% power for FNR smaller than 5%. With 400 subjects, the upper limit of the 95% confidence will exclude NLR > 0.52 if the NLR in the trial is smaller than 0.27; that is, the threshold (critical value) for rejecting the NLR null hypothesis is NLR≤0.27 (corresponding to FNR smaller than 6.5%). This evaluation is based on the large-sample variance of equation E and is adequate for selecting the total sample size for the trial. A complete power evaluation of trial power with and without an interim analysis requires a simulation study as described in section 9.5.1.

Based on Predictive Value of a Negative Test (NPV)

NPV is the probability that a subject with DSI \leq 18.3 does not have varices, and the false negative rate is defined from NPV according to equation D in **Table 9**. The goal is to ensure that *NPV is suitably large and FNR* is suitably small. NLR can also be written in terms of NPV. From equation D, *NLR* <0.27 corresponds to FNR <6.5% and a NPV over 0.937. Similarly, the critical value rules out NLR > 0.52, which corresponds to NPV > 0.885 (FNR < 11.5%). The study sample size gives 80% power under the hypothesis that *NLR* = 0.2, which corresponds to FNR < 5%.

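### The primary test rules out NLR > 0.52; it does not test superiority over LSM plus platelets, whose average NLR is 0.22 to 0.23, and 0.27 is a rejection threshold, not an average

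*Combined protocol and SAP*

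**What the plan says.** The justification column of Section 3 states that "The study is designed for superiority over current practice" and that "A critical value (cv) of 0.27 for NLR represents the average of results for these studies in ruling out large esophageal varices". Section 9.1.1 makes it a primary objective to find out whether the NLR for DSI ≤18.3 "is an improvement over the average value for NLR from 10 published studies of 2977 cases". It then sets the rule: "Improvement will be decided if the confidence interval for the observed NLR rules out NLR > 0.52". The choice of null is explained in the same place: "The null hypothesis of NLR = 0.52 is chosen to demonstrate improvement over the diagnostic accuracy of tests". That section also says that accuracy "is acceptable if the observed NLR is smaller than that observed in most previously published studies".

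Other parts of the document read differently:

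- Section 2.2.4 reports the pooled result of the ten studies as "negative likelihood ratio (NLR) 0.22, positive likelihood ratio (PLR) 1.33". Table 2 adds a mean of the study NLRs of 0.23.
- Section 9.2.1 defines 0.27 as a cut-off for the observed value: "the threshold (critical value) for rejecting the NLR null hypothesis is NLR≤0.27". Section 9 and the legend to Figure 10 agree.
- Section 9.5 again treats 0.27 as the average of the ten studies and computes comparator post-test odds from it.
- Sections 1.1, 4.1.3 and 9.4.2 describe the rule as validation against performance goals: an upper limit for NLR below 0.52, plus an observed-sensitivity criterion at 0.85. Section 9.4.2 adds that half of the LSM-plus-platelet studies would satisfy it.

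**The concern.** The stated inference and the test do not match. Excluding 0.52 cannot establish improvement over an average of 0.22 or 0.23, because the null is more than twice the value to be beaten. The one-sided 0.025 error rate protects against declaring success when the true NLR is 0.52. It gives no protection when DSI is merely as good as the published average. The study has one arm and plans no comparative NLR test.

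Labelling 0.27 as the average hides this gap. It makes the critical value look like the comparator's performance, so that an observed NLR below 0.27 reads as beating current practice. In a pivotal device study, the hypothesis section and endpoint justification govern what success may be said to show. As written, they would allow a report of superiority that was never tested.

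**Working it through.** **1. Reproduce the plan's 0.27.** Inputs from Section 9.2.1: sensitivity 0.90, specificity 0.50, 80 subjects with large varices, 320 without. Equation E of Table 9:

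- V = 0.90/(0.10 × 80) + 0.50/(0.50 × 320) = 0.1125 + 0.003125 = 0.1156; SE = 0.340.
- Critical value = 0.52 × exp(−1.96 × 0.340) = 0.267.
- Power at true NLR 0.20 = Φ(ln(0.52/0.20)/0.340 − 1.96) = 0.802, against 0.80 in Table 10.

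So 0.27 and N = 400 are correct as the threshold and sample size for rejecting 0.52.

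**2. Compute the average from Table 2.** Pooled counts: TP 298, FN 21, FP 1872, TN 786.

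- Sensitivity = 298/319 = 0.934; specificity = 786/2658 = 0.296; NLR = (21/319)/(786/2658) = 0.2226.
- Mean of the ten study NLRs (0.20, 0.23, 1.10, 0, 0.39, 0, 0.41, 0, 0, 0) = 0.233, SD 0.346.
- Other summaries: mean weighted by study size 0.218; median 0.10; random-effects estimate 0.31 to 0.34, depending on the continuity correction.

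None of these is 0.27. The null is 0.52/0.233 = 2.2 to 0.52/0.2226 = 2.3 times the average.

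**3. Compare with most published studies.** Seven of the ten NLRs are below 0.27, all seven with sensitivity above 0.85. An observed NLR just under 0.27 would be worse than most of the published results. Seven of ten also differs from the half stated in Section 9.4.2; Figure 10, on which that statement rests, is not available to check.

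**4. How often would a test equal to the comparator pass?** Simulation of 200,000 trials per setting used the score test of ratio 0.52, a random number of cases, 97.64% and 51.41% limits at N = 250, and a 96.07% limit at N = 400. The rule without an interim used 95%. At sensitivity 0.90, NLR 0.20 and 20% prevalence it gives 0.917 without and 0.853 with the interim; Table 12 has 0.916 and 0.855. At the pooled comparator accuracy:

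| Prevalence | With interim | Without interim |
|---|---|---|
| 20% | 0.565 | 0.605 |
| 15% | 0.420 | 0.464 |
| 11% | 0.281 | 0.327 |

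Reading the two futility conditions as both or either required moves these by at most 0.002. Using > or ≥ for the sensitivity criterion moves them by less than 0.001. Sensitivity to the accuracy assumed, at 20% with the interim:

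- Specificity 0.30: 0.41 at sensitivity 0.92, 0.79 at 0.95.
- Sensitivity 0.93: 0.28 at specificity 0.25, 0.76 at 0.35.

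Table 12 shows the same property. At 20% prevalence with the interim, a true NLR of 0.30, worse than the stated average, passes with probability 0.417, 0.348 and 0.124 at sensitivity 0.85, 0.90 and 0.95.

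**5. What a test against the average would need.** By equation E at N = 400 and one-sided 0.025, power against 0.22 is 4.7% at a true NLR of 0.20 and 42% at the HALT-C value of 0.0926. Power of 80% at 0.0926 needs about 1,007 subjects against 0.22, or 911 against 0.23.

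**6. Section 9.5 odds.**

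- At 11% prevalence: 0.2226 × (0.11/0.89) = 0.0275, not 0.033; the reduction in odds is 1/0.2226 = 4.5-fold, not 3.6-fold.
- At 20%: 0.2226 × 0.25 = 0.056, not 0.0675.
- With the mean of 0.233: 0.0288, 4.3-fold and 0.058.

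The HALT-C odds of 0.0102 and 0.0225 stay lower, so the direction of the comparison holds.

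**The case against.** The best defence is that this is a matter of words. The rule against 0.52 is stated consistently, the primary objective is to validate a cut-off, and the endpoint column of Section 3 calls the criterion a performance goal. Section 9.1.1 says how improvement will be decided, and Section 9.4.2 openly says that current tests can pass. That is true, and it is why no change to the test is needed. It does not cure the mismatch, because the improvement claim stands in the hypothesis section itself. A standard that the comparator often meets cannot show improvement over the comparator. The sensitivity criterion does not help either, since pooled comparator sensitivity is already 0.93.

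Two caveats stand. First, the averages are crude: five of the ten NLRs are zero because no case was missed. Random-effects intervals reach 0.52 or 0.56, depending on the correction. It is therefore not claimed that 0.52 is implausible for current practice, only that it is not the stated average. Second, the pass probabilities assume that accuracy measured almost entirely in Child-Pugh A cirrhosis carries over to a population that includes F3 fibrosis and Child-Pugh B.

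**Conclusion.** The concern holds. The superiority and improvement claims in Sections 3 and 9.1.1 do not follow from the prespecified rule, and 0.27 is wrongly labelled as an average in Sections 3 and 9.5. The rule supports one conclusion: that NLR above 0.52 has been ruled out and the observed-sensitivity criterion met. At the design prevalence, a test no better than the pooled comparator would succeed more than half the time, if its accuracy transfers. That figure is sensitive to the accuracy and prevalence assumed. The textual contradiction and the mislabelled figure depend on neither. The sample size and critical value are correct for the null actually tested. The text must be corrected, preferably before any unblinding, because it determines what a positive result may be said to show.

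**What to change.** - In Sections 3, 9.1.1 and 9.4.2, replace the superiority and improvement language. Say that DSI meets the absolute performance goal if the upper limit for NLR is below 0.52 at the confidence level set in Section 9.5.1 and the observed-sensitivity criterion is met. Add that this does not show superiority over LSM plus platelets.
- In Sections 3 and 9.5, replace the average of 0.27 with 0.22 (pooled) and 0.23 (mean), labelled as crude Table 2 figures. Keep 0.27 only as the approximate critical value.
- Delete the Section 9.1.1 comparison with most published studies, and reconcile the half in Section 9.4.2 with Table 2.
- Recompute the comparator odds in Section 9.5. Reword its headings on improved performance, lower FNR and lower miss rate, so that they are not presented as consequences of validation.
- In the same edit, though it is a separate matter, state one sensitivity criterion. It is > 0.85 in Sections 1.1, 3, 4.1.3 and 9.5, ≥ 0.85 in Sections 9 and 9.5.1, and both in Section 9.4.2. With the planned 80 cases, 68/80 is exactly 0.85. That count has probability 0.124 at a true sensitivity of 0.85 and 0.047 at 0.90.

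The cost is protocol and SAP wording plus a few lines of arithmetic. The test, sample size and interim analysis do not change. The price to the sponsor is a weaker claim on success. If superiority is really wanted, it needs a test against the published average and a sample size of the order shown above.
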